	
In addition, MTX treatment should be given at a stable dose ≥ 10 mg/week (for at least 4 weeks prior to randomization). The maximal dose of methotrexate should not exceed a total of 20 mg/week. MTX treatment should be associated with folic acid at a dose ≥ 5 mg/week.
 
For the anti-TNFα therapy, the following wash-out period will be required:
 
 ○ 30 days prior to randomization for adalimumab and etanercept ○ 2 months prior to randomization for infliximab, certolizumab pegol, golimumab 
 ▪ Patients with the following hematological and biochemical laboratory parameters obtained within 14 days prior to baseline: 
 ○ Hemoglobin > 9.0 g dL⁻¹; ○ Absolute neutrophil count ≥ 1000 mm⁻³; ○ Platelets $\geq 100,000$ mm⁻³; ○ Total serum creatinine ≤ 1.3 x ULN (upper limit of normal); ○ Creatinine clearance > 50 mL min⁻¹ by the Cockcroft-Gault equation within 60 days prior to baseline; ○ Total serum bilirubin < 1.5 x ULN; ○ Alkaline phosphatase, AST (SGOT) and ALT (SGPT) < 1.5 x ULN; ○ Negative screening for TB and HIV, HCV, HBV ▪ Patients are able and willing to comply with study visits and procedures as per protocol; ▪ Patients should understand, sign and date the written voluntary informed consent form at the screening visit prior to any protocol-specific procedures are performed; ▪ Patients should be affiliated to a social security regimen (for French sites only); ▪ Females and males receiving the study treatment and their partners must agree to use a highly effective contraceptive method during the study and for 6 months after end of study or early termination. Contraception should be in place at least 2 weeks prior to screening. Women must be surgically sterile or if of childbearing potential must use a highly effective contraceptive method. Women of childbearing potential (WOCBP) will enter the study after confirmed menstrual period and a negative pregnancy test. Highly effective methods of contraception include true abstinence, intrauterine device (IUD) or hormonal contraception aiming at inhibition of ovulation, intrauterine hormone releasing system, bilateral tubal ligation, vasectomized partner. True abstinence is defined when this is in line with the preferred and usual lifestyle of the patient. In each case of delayed menstrual period (over one month between menstruations) confirmation of absence of pregnancy is required. This recommendation also applies to WOCBP with infrequent or irregular menstrual cycle. Female and male patients must not be planning pregnancy and male patients should use condom and must not donate sperm during the trial and for 6 months post completion of their participation in the trial. 
Exclusion Criteria:
 
The following criteria should be checked at the time of screening. If ANY exclusion criterion applies, the patient will not be included in the study:
 
 ▪ Patient with a known positive anti-double stranded deoxyribonucleic acid (DNA [anti-dsDNA]) and confirmed diagnosis of systemic lupus erythematosus (SLE); ▪ Patients with active infection or the following history of infection(s) (the list is not exhaustive): 
 ○ Active infection (except benign infections, according to investigator's opinion) within 14 days prior to inclusion. ○ Serious infection, defined as an infection requiring hospitalization or IV infusion of anti-infective agents in the 2 months prior to inclusion. ○ A history of opportunistic, recurrent or chronic infections that, in the investigator's opinion, could render this study detrimental to the patient. • Patients who have received or are expected to receive a live (including attenuated) vaccine within 3 months prior to baseline; ▪ Acute, chronic or history of clinically relevant (as per investigator's judgement) pulmonary, cardiovascular, hepatic, pancreatic or renal functional abnormality, encephalopathy, neuropathy or unstable CNS pathology such as seizure disorder, angina or cardiac arrhythmias, active malignancy or any other clinically significant

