
Study n° ABX464-301	Clinical Phase IIa Type of Study Safety, Tolerability, Efficacy Study
	
medical problems as determined by physical examination and/or laboratory screening tests and/or medical history;
 
 ▪ Acute, chronic or history of immunodeficiency or other autoimmune disease; ▪ Patient previously treated with any (approved or investigational) non-anti-TNF biological disease-modifying antirheumatic drugs (bDMARDs), and targeted DMARDs (tDMARDs) prior to baseline. These treatments include: IL-6 antagonists, Janus Kinase (JAK) inhibitors, cytotoxic T lymphocyte-associated molecule CTLA-4Fc Chimera, rituximab; ▪ Patient treated with systemic corticosteroids >10 mg/day during the 2 weeks prior to and at randomization; IV or IM injections of glucocorticoids 4 weeks prior to randomization and IA glucocorticoids 2 weeks prior to randomization; ▪ Patients treated with other immunosuppressive drugs; ▪ History of malignancy (other than resected cutaneous basal cell or squamous cell carcinoma that has been treated with no evidence of recurrence) unless it has been treated and a cure is achieved for at least 5 years; ▪ Serious illness requiring systemic treatment and/or hospitalization within 3 weeks prior to baseline; ▪ Pregnant or breast-feeding woman; ▪ Illicit drug or alcohol abuse or dependency; ▪ Use of any investigational or non-registered product within 3 months or within 5 half-lives preceding baseline, whichever is longer; ▪ Any condition, which in the opinion of the investigator, could compromise the patient's safety or adherence to the study protocol.

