- Illicit drug or alcohol abuse or dependency;
- Use of any investigational or non-registered product within 3 months or within 5 half-lives preceding baseline, whichever is longer;
- Any condition, which in the opinion of the investigator, could compromise the patient's safety or adherence to the study protocol.

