5. STUDY ASSESSMENTS AND PROCEDURES

5.1. Study Flow Chart

A detailed study flow chart (with all assessments) is displayed hereafter.

	Screening Period	Study Treatment Period						Follow-up Period
	D-30 to D-1	D0	D7	D14	D28	D56	D84	D105
		W0	W1	W2	W4	W8	W12	W15
Time Window (time between two visits ≤ 30 days)			± 2 days	± 2 days	± 2 days	± 2 days	± 2 days	± 2 days
	Screening	Baseline	V1	V2	V3	V4	V5	EOS
Obtained Informed Consent	X							
Check of IN/EX Criteria	X							
Medical History	X							
Height Measurement (cm)	X							
Body Weight (kg)	X	X	X	X	X	X	X	X
Physical Examination	X	X	X	X	X	X	X	X
Vital signs	X	X	X	X	X	X	X	X
Concomitant Medications	X	X	X	X	X	X	X	X
ECG (12 lead)	X	X					X	X*
Blood Pregnancy test (WOCBP)	X				X	X	X	X
Urine Pregnancy test (WOCBP)		X						
Randomization		X						
ABX464/placebo treatment dispensation		X			X	X		
Hematology + Biochemistry#	X#	X	X	X	X	X	X	X
Blood samples drug PK (pre-dose)				X		X		X**
Blood samples drug PK (1-, 2- & 3- hours post-dose)		X		X		X		
Blood samples for Cytokines (gel tube)		X	X	X	X	X	X	
Blood samples for Cytokines (Truculture® tube)		X				X		
Blood samples for flow cytometry cells count***		X				X		
Blood samples for CRP, ESR	X	X	X	X	X	X	X	
Blood samples for miR-124 (Paxgene® tube)		X				X		
Tender Joint Count (28)	X	X		X	X	X	X	
Swollen Joint Count (28)	X	X		X	X	X	X	
Patient Global Assessment of Disease (PtGA-VAS)	X	X		X	X	X	X	
Patient assessment of Joint Pain (Pain-VAS)		X		X	X	X	X	
Investigator Global Assessment of Disease (PrGA-VAS)		X		X	X	X	X	
Health Assessment Questionnaire – Disease Index (HAQ-DI)		X		X	X	X	X	
Functional Assessment of Chronic Illness Therapy (FACIT)-Fatigue		X		X	X	X	X	
Patient diary (dispensation/check)		X	X	X	X	X	X	
Adverse Events recording	X	X	X	X	X	X	X	X
Follow-up Headache Questionnaire in case of persistent headache (see section 5.3.2)			X (throughout the study, if needed)					
Dermatologist consultation in case of skin effect (see section 5.3.2)			X (throughout the study, if needed)					

#Tests of TB, HIV, HCV, HBV only at screening; *ECG at EOS visit in case of early termination only; **trough levels PK samples; ***Only in French Coordinating Investigator's Site; Two visits should not be conducted more than 30 days apart

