5.2.1. Screening Visit (within 30 days prior to Baseline/Day 0)

The patient will be informed about the general aspects of the study and will sign the informed consent form. The patient number will be allocated once the patient is created in the eCRF. Only when consent has been given may further study procedures be carried out.

During the screening phase, the following assessments will be performed:

- Signed informed consent form;
- Demographic data: year of birth and gender;

- Inclusion/exclusion criteria will be verified globally, including disease confirmation according to the revised 2010 ACR-EULAR classification criteria with at least one positive criteria among the following: Rheumatoid Factor (RF), Anti-Citrullinated Peptide Antibody (ACPA) or bone erosion;
- Body weight and height;
- Medical history;
- Physical examination and vital signs;
- 12 leads ECG;
- Hematology and Biochemistry panel;
- Blood pregnancy test for all women of childbearing potential;
- Blood samples for testing TB, HIV, HCV, and HBV;
- Blood samples for acute phase reactants;
 - C-Reactive Protein (CRP)
 - Erythrocyte Sedimentation Rate (ESR)
- Tender/painful joint count (TJC) (28);
- Swollen joint count (SJC) (28);
- Patient global assessment of disease (PtGA);
- If the patient was treated by anti- TNF α therapy, confirm the adequate wash-out of the anti-TNF α therapy has started at least and collect the reason of anti- TNF α therapy discontinuation (i.e. intolerance, primary or secondary resistance):
 - 1 month prior to screening for adalimumab and etanercept
 - 2 months prior to screening for infliximab, certolizumab pegol, golimumab
- Record all medications received within 3 months prior to baseline and note if the medication is continuing; Record all RA medication without time limitation;
- Adverse Event reporting;
- Schedule next patient visits.

NB: If patient meets all eligibility criteria, has an adequate wash-out of previous therapies and laboratory results are available, the baseline visit could be performed on the same day as screening visit. In that case, it is not necessary to repeat twice the assessments required at both visits. The following additional baseline assessments have to be performed:

- Urine Pregnancy test for all women of childbearing potential;
- Pharmacokinetics blood samples at 1h-, 2h- and 3-hours post-dose;
- Patient assessment of joint pain (Pain-VAS);
- Investigator global assessment of disease (PrGA);

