5.2.2. Baseline (First dosing day / Day 0)

- Physical examination and vital signs;
- Body weight;
- 12 leads ECG;
- Hematology and Biochemistry panel;
- Urine Pregnancy (β -HCG) test for all women of childbearing potential;

- Pharmacokinetics blood samples at 1h-, 2h- and 3-hours post-dose;
- Blood samples for acute phase reactants (CRP & ESR);
- Blood (gel tubes and Truculture® tubes) samples for cytokines determination;
- Blood samples (Paxgene® tubes) for miR-124 dosage;
- Blood samples for flow cytometry cells count (including at least B & T lymphocytes, myeloid cells and macrophages) (only in the Coordinating Investigator's site);
- Tender/painful joint count (28) (TJC28);
- Swollen joint count (28) (SJC28);
- Patient global assessment of disease (PtGA);
- Patient assessment of joint pain (Pain-VAS);
- Investigator global assessment of disease (PrGA);
- Disability index of the healthy assessment questionnaire (HAQ-DI);
- Functional Assessment of Chronic Illness Therapy (FACIT)-Fatigue;
- Record any concomitant medications;
- Confirm the wash-out of the anti-TNF α therapy is complete;
- Adverse Events reporting;
- Randomization;
- Dispense study treatment to patient and instruct how to take them (first dosing at site);
- Dispense patient diary (for treatment compliance and adverse event recording) and instruct how to complete them;
- Schedule next patient visits.

5.2.3. Week 1 / Day 7 (+/- 2 days) - Visit 1

- Physical examination and vital signs;
- Body weight;
- Hematology and Biochemistry;
- Blood samples for cytokines determination
- Record any concomitant medications;
- Check treatment compliance on patient diary;
- Adverse Events reporting;
- Schedule next patient visits.

5.2.4. Week 2 / Day 14 (+/- 2 days), Week 4 / Day 28 (+/- 2 days), Week 8 / Day 56 (+/- 2 days), Week 12 / Day 84 (+/- 2 days) - Visits 2, 3, 4, 5

- Physical examination and vital signs;
- Body weight;
- 12-leads ECG (D84 only);
- Hematology and Biochemistry panel;
- Blood pregnancy test for all women of childbearing potential (except on Week 2);
- Pharmacokinetics blood samples pre-dose, 1h-, 2h- and 3-hours post-dose (Week 2 / Day 14 and Week 8 / Day 56 only);
- Blood samples for acute phase reactants (CRP, ESR);
- Blood samples (gel tubes) for cytokines determination;
- Blood samples (Truculture® tubes) for cytokines determination at Week 8 only;
- Blood samples (Paxgene® tubes) for miR-124 qPCR dosage (Week 8 only);

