5.3.5. Hematology and biochemistry

For hematology and biochemistry panels, local laboratory will be used.

Each laboratory value that is outside of the institution's normal range will be identified. The Investigator will be responsible for assessing the clinical significance of laboratory abnormalities. If the Investigator is uncertain about the clinical significance of a laboratory abnormality, he/she will consult with the Sponsor medical monitor.

The Investigator should follow any clinically significant laboratory abnormalities until resolution.

The Table 1 displays the clinical laboratory parameters that must be measured.

Table 1: Laboratory Tests

HEMATOLOGY	BIOCHEMISTRY
Hemoglobin	Sodium
Hematocrit	Potassium
WBC	Chloride
Neutrophils	Calcium
Lymphocytes	Phosphate
Monocytes	Glucose
Eosinophils	BUN or urea
Basophils	Creatinine
Platelet count	AST / SGOT
ESR	ALT / SGPT
Prothrombin time and/or INR*	Alkaline phosphatase
Fibrinogen*	GLDH
	LDH
	Lipase
	Total cholesterol
	HDL cholesterol
	LDL cholesterol
	gGT
	Total bilirubin
	Total protein
	Albumin
	CRP
	T3, T4, TSH (for French sites only)
	Troponin I & T*

Tests of TB (Quantiferon TB Gold Plus), HIV (anti-HIV Ab), HCV (anti-HCV Ab), HBV (HBsAg, anti-HBs Ab), anti-HCV Ab, will be performed only at screening. * Except at Week 1 & 2

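### Creatinine clearance at entry may be 60 days old, so a patient can qualify although the fresh creatinine gives 50 mL/min or less (minor)

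*Protocol*

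**What the plan says.** The laboratory inclusion criterion appears in the same form in the protocol synopsis, Protocol 4.2.1 and SAP 3.2.1. Its header covers values "obtained within 14 days prior to baseline". Two renal items sit under it:

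- serum creatinine no higher than 1.3 x ULN, with no window of its own;
- creatinine clearance above 50 mL/min, "by the Cockcroft-Gault equation within 60 days prior to baseline".

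Screening may take place on any day from Day -30 to Day -1, or on the same day as baseline if results are available (Protocol 5.1 and 5.2.1). In the flow chart the row "Check of IN/EX Criteria" is marked at screening only. The Day 0 list (Protocol 5.2.2) includes a "Hematology and Biochemistry panel" and a check that anti-TNF wash-out is complete, but no clearance calculation and no renewed eligibility check.

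Methotrexate is mandatory in every arm (Protocol 5.12.1). Appendix 5, the methotrexate product information, says in its section 4.4 that renal impairment raises methotrexate concentrations. Its section 4.2 halves the dose at a clearance of 30 to 59 mL/min.

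**The concern.** The two windows can give two different clearances for one patient, and the plan has no rule that the more recent one decides. If the 60-day wording is an exception, an older value above 50 satisfies the criterion whatever the fresh creatinine implies. If the 14-day header governs, the 60-day phrase has no meaning. Either way the text needs correcting.

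What is at stake is mainly safety at entry. The sponsor chose 50 mL/min as its limit in patients who all take a renally cleared drug, so the limit is best applied to the newest value in hand. There is also a practical side. Protocol 8.1.1 treats failure to meet an inclusion criterion as a major deviation, which removes a patient from the per-protocol set. Sites and the blind review should not have to guess which window applies.

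**Working it through.** The plan states no figure to reproduce here. Two things need checking: whether the situation can arise in normal conduct, and whether the creatinine limit already prevents it.

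**1. Timing.** From Day -30 to Day -1 there are 30 possible screening days. On Day -30 to Day -15, which is 16 of them, the screening panel is too old for the 14-day items but still valid for clearance under the 60-day wording. A second creatinine is then required, and no step turns it into a clearance. No historical record from before screening is needed. The 16 of 30 counts calendar days and is not a probability.

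**2. Formula.** Cockcroft-Gault clearance in mL/min = (140 - age) x weight in kg / (72 x creatinine in mg/dL), multiplied by 0.85 for women. The age range of 18 to 75 years is from Protocol 4.2.1. The documents give neither body weights nor a ULN for creatinine, so I assume a ULN of 0.9 to 1.1 mg/dL for women and, where used, 1.2 mg/dL for men.

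**3. Illustration: woman, 70 years, 60 kg.** (140 - 70) x 60 x 0.85 / 72 = 49.58, so clearance = 49.58 / creatinine.

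| Creatinine (mg/dL) | Clearance (mL/min) |
|---|---|
| 0.95 (older value) | 52.2, passes |
| 0.99 | 50, the limit |
| 1.05 (fresh value) | 47.2, below the limit |

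The rise is 1.05 / 0.95 = 1.105, or 10.5%. The fresh value passes the creatinine criterion throughout the assumed range, since 1.3 x ULN is 1.17, 1.30 or 1.43 mg/dL for a ULN of 0.9, 1.0 or 1.1. It lies above the normal range at a ULN of 0.9 or 1.0 but within it at 1.1.

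**4. Does the creatinine limit protect the clearance limit in general?** For a woman of 70 with creatinine exactly at 1.3 x ULN, clearance is 50 or less when weight is at or below 50 x 72 x 1.3 x ULN / (70 x 0.85):

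| Assumed ULN (mg/dL) | Weight (kg) |
|---|---|
| 0.9 | 70.8 |
| 1.0 | 78.7 |
| 1.1 | 86.5 |

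Other patients with creatinine at 1.3 x ULN:

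| Patient | Assumed ULN (mg/dL) | Clearance (mL/min) |
|---|---|---|
| Woman, 65 years, 60 kg | 1.0 | 40.9 |
| Man, 75 years, 70 kg | 1.2 | 40.5 |
| Woman, 45 years, 70 kg | 1.0 | 60.4 |
| Man, 45 years, 70 kg | 1.2 | 59.2 |

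The creatinine limit therefore does not enforce clearance above 50 in older or lighter patients, while in younger or heavier ones it usually does.

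**The case against.** The strongest reply is that the text does not authorise choosing an older value over a newer one. The header can be read as covering clearance too, and a fresh 47 mL/min is itself a clearance inside 60 days that fails. That makes the wording ambiguous rather than permissive. The point has force, but an ambiguity in a numerical entry limit still needs resolving, and the separate window is hard to explain except as an exception.

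Second, Protocol 5.7 randomizes only patients who meet all criteria, and 8.1.1 bars randomization when a major deviation is present at baseline. These rules enforce the criterion as written. If the criterion accepts the older value, they do not exclude the patient.

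Third, there are backstops. The renal exclusion extends to "medical problems as determined by physical examination and/or laboratory screening tests and/or medical history". Another exclusion covers "Any condition, which in the opinion of the investigator, could compromise the patient's safety". Protocol 5.3.5 adds "Each laboratory value that is outside of the institution's normal range will be identified", and biochemistry is repeated at Day 0 and every later visit. These are real and reduce the risk, but they rest on judgement, carry no clearance figure, and would not flag a creatinine that is still within the normal range.

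Fourth, the harm is modest. Methotrexate is continued background treatment, stable for at least four weeks before randomization. The protocol does not say that the 50 mL/min limit was chosen because of methotrexate. Both illustrated values, 52.2 and 47.2, fall in the same 30 to 59 mL/min dose band of Appendix 5. All of this stands, and it is why the point is minor.

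Finally, changing an eligibility criterion is more than an edit. Protocol 9.1.2 sends amendments to the ethics committee, and SAP 1.1 says recruitment was under way. That cost is fair to count.

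**Conclusion.** The concern holds as a minor one. As most naturally read, the criterion admits a patient whose fresh creatinine gives a clearance of 50 mL/min or less, and no other rule in the plan prevents it by number. The conclusion about the text rests on treating the 60-day phrase as an exception to the 14-day header. The numerical illustrations rest on assumed ages, weights and ULNs.

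The number of patients affected is probably small among up to 60 randomized, and it cannot be estimated from the documents. The gain from correcting it is that the stated entry limit is actually met at entry. In the illustrated case the methotrexate dose category does not change. The endpoints and the power calculation are unaffected.

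**What to change.** Remove the 60-day phrase from the protocol synopsis, Protocol 4.2.1 and SAP 3.2.1. State that Cockcroft-Gault clearance is calculated from the serum creatinine taken in the 14 days before baseline, using age and screening weight. Leave the limit of 50 mL/min as it is.

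No sample or visit is added, because the 14-day creatinine, weight, birth year and sex are already collected. The costs are wording changes in three places, the amendment procedure that goes with an eligibility change (it can be bundled with another amendment), and possibly a few more screen failures among patients near the limit.

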	
least one abnormal value will be tabulated (counts and percents) for each parameter in summary shift tables by group.
 
Efficacy:
 
Analysis of efficacy data will be carried out in the Full Analysis Set in which subjects who prematurely terminate the study will be considered failures.
 
The primary efficacy endpoint of the study, the ACR20 response rate, will be compared in subjects who received a given dose of ABX464 or placebo by likelihood ratio chi-square test on a 10% two-sided level. The result of the test will be interpreted in a descriptive manner therefore no adjustment for the multiple comparison is applied.
 
In addition, descriptive statistics will be presented by treatment arm for all secondary efficacy variables for each measurement timepoints separately for the two study groups.
 
These statistics include:
 
 ○ Continuous variables: mean, standard deviation, minimum and maximum, stratified 95% confidence intervals, median and quartiles will be presented. ○ Categorical variables: counts, rates and stratified 95% confidence intervals for the rates will be calculated. 
In addition to descriptive statistics, mixed model analysis of covariance will be conducted for the following measurements:
 
 ○ The change from baseline in DAS28-CRP and DAS28-ESR ○ The change from baseline in the individual components of the ACR20 response (CRP, TJC(28), SJC(28), Pain-VAS, PtGA, PrGA, HAQ-DI) and in ESR ○ The change from baseline in SDAI and CDAI scores ○ The change from baseline in miR-124 in total blood at Week 8 
In this model, treatment will be fixed effect, subjects will be random effect, and baseline values of the respective measurements will be covariates. Other explanatory variables will also be allowed to be included in the model. In order to normalize eventual skewed distributions transformation of the data will also be considered. Study groups will be compared within this model framework. All p-values will be interpreted in a descriptive manner.
 
Pharmacokinetics:
 
Even though the PK characteristics of ABX464 are well documented in healthy volunteers and HIV-infected subjects, the RA condition deserves a population PK exploration.
 
Hence, PK determinations will be performed in subjects enrolled in this study. The PK evaluation consists of pre-dose samples on Week 2 and Week 8, 1-, 2- and 3-h post-dose samples on Baseline, Week 2 and Week 8, and trough-dose sample on EOS visit.
 
The following PK parameters will be derived for ABX464, NGlcABX464 for each subject:
 
 ○ C_{max}, t_{max}: the maximum plasma concentration (C_{max}) and the time taken to reach C_{max} (t_{max}) will be obtained directly from the concentration-time data. ○ AUC_{0-τ}: the area under the concentration-time curve from time zero to the time of dosing interval τ (12 h post-dose for ABX464 and NGlcABX464). If no concentration can be measured at this time point, AUC_{0-last} (from time zero to the last quantifiable concentration) will be calculated. Both parameters will be presented independently. For both parameters, a linear trapezoidal method will be used 		

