5.3.6. Pharmacokinetics

Blood samples will be collected in all patients for PK assessment.

Sampling will be performed:

- pre-dose on Week 2 / Day 14 and Week 8 / Day 56;
- 1-, 2- and 3-hours post-dose on Baseline / Day 0, Week 2 / Day 14 and Week 8 / Day 56 and
- trough levels at the End of Study Visit (Week 15 / Day 105).

The PK samples will be kept in the local laboratory, at -20°C until pick-up.

Patient data will be pooled with data obtained in previous clinical studies in order to build a population pharmacokinetic models for ABX464 and its metabolite.

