5.4. Description of investigational treatment

The study treatment that will be administered to patients enrolled in this Phase IIa study consists of capsules containing ABX464 or its matching placebo given orally once daily for 12 weeks.

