5.12. Prior and Concomitant Medication

5.12.1. Mandatory concomitant treatment

- ABX464 or its matching placebo administered once daily;
- MTX \geq 10 mg/week, at stable dose, throughout the study; the **maximal dose of methotrexate should not exceed a total of 20 mg/week**
- Folic acid \geq 5 mg/week post MTX dose, to minimize MTX toxicity.

Potential Drug-Drug Interactions (DDIs) with methotrexate:

ABX464 is mainly metabolized by CYP1A2 and glucuro-conjugated. Methotrexate undergoes hepatic and intracellular metabolism to polyglutamated forms.

Multiple DDIs have been documented with methotrexate. In this study, potential methotrexate interactions on ABX464 will be sought using an on-going PK modelling approach.

For documented DDIs with methotrexate, please refer to the Appendix 5.

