8.3. Pharmacokinetics

Population PK data analysis will be performed via three steps:

- Data preparation and exploratory: The analysis dataset will be created and formatted according to MONOLIX or NONMEM requirement using SAS®. An exploratory analysis by visual inspection of PK profiles/dose normalized PK profiles in natural and semi-log scale will be performed in order to anticipate the type of PK model (number of compartments, linear or saturable elimination, etc)
- Population PK model development: A PopPK model consists of four basic components:
 - The structural PK model, which defines the PK parameters and describes the plasma concentration-time profiles of ABX464 and its metabolite.
 - The inter-individual variability model component, which describes the inter-individual variability of PK parameters in the population
 - The residual error model component, which describes the underlying distribution of the error in the measured concentrations.
 - The covariate model component, which describes the influence of covariates such as demographic data on PK parameters.

The search for the final model will follow the following strategy:

- Selection of the simplest structural model, which predicts the plasma concentration as a function of time and dose, based on smallest objective function and by the pattern in the residual plots. The best estimation method, the most appropriate inter-individual variability (IIV) models, and the residual error model, are identified. The resulting model is called BASE model.
- Test of influence of selected covariates.

- Refinement of inter-individual variability model and residual error models
- Model validation: Goodness of fit plots will be assessed for each important step of model building. For the final model, a visual predictive check (an evaluation graph based on simulation) will be provided.

Data will be prepared using SAS version 9.2. Population analysis will be performed using MONOLIX version 2018 R1 or NONMEM version 7.2. Graphs will be provided using SAS.

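### The synopsis plans a 12 h AUC for a once-daily drug sampled only to 3 h, so it cannot be computed and the fallback is at most an AUC over 0–3 h

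*Protocol*

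**What the plan says.** The pharmacokinetics paragraph of the protocol synopsis lists parameters to be derived for each patient, for ABX464 and its glucuronide. Cmax and tmax are read from the observed data. AUC runs from zero to the end of the dosing interval, which is given as "12 h post-dose for ABX464 and NGlcABX464". If there is no concentration at that time, AUC to the last quantifiable concentration is calculated instead. Both AUCs use the linear trapezoidal rule and are to be reported separately.

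Other parts of the protocol bear on this:

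- **Regimen.** Section 5.4 describes capsules "given orally once daily for 12 weeks", and section 5.12.1 lists "ABX464 or its matching placebo administered once daily".
- **Sampling.** Section 5.3.6 schedules samples "1-, 2- and 3-hours post-dose on Baseline / Day 0, Week 2 / Day 14 and Week 8 / Day 56", plus a pre-dose sample at Weeks 2 and 8 and one sample at the end-of-study visit. The flow chart (section 5.1) and the synopsis agree.
- **Analysis.** Section 8.3 opens "Population PK data analysis will be performed via three steps" and describes only model building and validation. It mentions no trapezoidal AUC and does not list the exposure measures that the model will deliver.
- **SAP.** Section 11.4 says that the CRO will not conduct the PK analysis. Section 4.2.2 lists plasma concentrations as the PK endpoints, as does protocol section 2.4.

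**The concern.** A 12 h dosing interval is what twice-daily dosing would give, yet every description of the regimen in this protocol is once daily. The AUC also needs a concentration at 12 h, and no sample is planned between 3 h and the next dose. The rule therefore fails on both the length of the interval and the data needed to fill it.

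Pharmacokinetics of the drug and its metabolite is a secondary objective. The synopsis is the only place that defines per-patient PK parameters, and neither section 8.3 nor the SAP corrects it. An analyst following it would report an empty AUC over the dosing interval beside an AUC to the last concentration that stops about one hour after the usual peak. Neither describes exposure over a day of treatment.

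**Working it through.** **1. The stated interval.** Dosing interval = 24 h ÷ doses per day.

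- Once daily (protocol 5.4, 5.6.1, 5.12.1): 24 ÷ 1 = 24 h.
- The synopsis figure of 12 h needs 24 ÷ 2, that is, two doses a day. It is not reproduced from the planned regimen.

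**2. The samples available.** Table 2 (protocol 5.3.8) gives PK volumes drawn in 2 mL tubes, which allows a check on the schedule.

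| Visit | Volume (mL) | Tubes | Sample times |
|---|---|---|---|
| Day 0 | 6 | 6 ÷ 2 = 3 | 1, 2, 3 h |
| Day 14 | 8 | 8 ÷ 2 = 4 | pre-dose, 1, 2, 3 h |
| Day 56 | 8 | 8 ÷ 2 = 4 | pre-dose, 1, 2, 3 h |
| End of study | 2 | 2 ÷ 2 = 1 | single sample |

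Every tube is accounted for, and none is at 12 h or 24 h. The end-of-study sample comes three weeks after the last dose (section 5.2.5), so it lies outside any dosing interval.

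**3. The fallback.** The 12 h value is missing by design, so the fallback applies to every patient at every PK visit. It ends at 3 h, or earlier if the 3 h value is not quantifiable. Its largest share of clock time is:

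- of the stated interval: 3 ÷ 12 = 25%;
- of the once-daily interval: 3 ÷ 24 = 12.5%.

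Day 0 has no scheduled pre-dose sample, so its value at time zero must be taken as zero.

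**4. Can the trapezoid reach 24 h?** At Weeks 2 and 8 the pre-dose value could stand in for the 24 h value if the patient is at steady state. The documents do not state that assumption. The last segment would be one straight line over 24 − 3 = 21 h. This still gives no 12 h value, and it is not available on Day 0.

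**5. Share of exposure (illustration only).** The documents give no half-life, so half-lives from 1.5 to 24 h are assumed. The model is one-compartment with first-order absorption:

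C(t) ∝ [ka/(ka − ke)] · [exp(−ke·t) − exp(−ka·t)], with ke = ln 2 ÷ half-life.

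Here ka is chosen so that tmax = ln(ka/ke)/(ka − ke) = 2 h, the approximate time of the ABX464 peak in the first-in-human study (section 1.2.6). Columns two and three are for a single dose. The last column is at steady state, with the pre-dose value used at both 0 and 24 h.

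| Assumed half-life (h) | Trapezoid 0–3 h ÷ AUC 0–12 h | Trapezoid 0–3 h ÷ AUC 0–24 h | Trapezoid 0–24 h ÷ true AUC 0–24 h |
|---|---|---|---|
| 1.5 | 0.43 | 0.42 | 2.17 |
| 4 | 0.33 | 0.29 | 1.55 |
| 8 | 0.28 | 0.20 | 1.18 |
| 12 | 0.25 | 0.17 | 1.09 |
| 24 | 0.23 | 0.13 | 1.02 |

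The 0–3 h AUC captures about 13–42% of 24 h exposure, depending on half-life. The trapezoid stretched to 24 h overstates exposure by about 2% to 117%.

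**The case against.** The strongest reply is that this is stray synopsis text. Section 8.3 specifies population modelling, section 5.3.6 pools these data with earlier studies for that model, and sparse sampling suits it. The listed PK endpoints are concentrations, so no endpoint depends on an AUC. This stands and limits the impact. It does not repair the synopsis, because section 8.3 never says that an individual AUC will come from the model.

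A reader might also infer more than the documents support:

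- **That a 24 h AUC is equally impossible.** It is not. With steady state assumed, a coarse version can be computed at Weeks 2 and 8. Only the 12 h AUC is strictly out of reach.
- **That a partial AUC would be passed off as full exposure.** The synopsis gives the fallback its own name and definition and reports it separately.
- **That slow absorption makes the dose groups incomparable.** The only timing given is a peak at about 2 h in all first-in-human dose groups, inside the sampled window. Those were single doses in healthy volunteers, so slower absorption in these patients is possible but not shown. Both active groups share the same sampling times, so a labelled 0–3 h AUC can be compared between them as early exposure.
- **That observed Cmax and tmax are worthless.** They can be obtained, though tmax can take only sampled times and Cmax is the highest sampled value.

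**Conclusion.** The AUC rule in the synopsis is wrong as written. Its 12 h interval contradicts once-daily dosing, and under the planned schedule the 12 h AUC cannot be computed by the stated method for any patient. The fallback always applies and covers at most 25% of the stated interval and 12.5% of the once-daily interval. These two figures are clock time, follow from the documents alone, and should not be read as the fraction of exposure captured. The exposure ranges in the working rest on an assumed one-compartment model and assumed half-lives, and they only show that the captured share is not stable.

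The consequence is limited to secondary PK reporting. The TEAE and ACR20 analyses are unaffected. The point is worth correcting because the only per-patient PK definitions in the plan cannot be followed.

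**What to change.** Reconcile the synopsis PK paragraph with the once-daily regimen, the sampling schedule in section 5.3.6 and section 8.3:

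1. Delete the 12 h trapezoidal AUC over the dosing interval.
2. State in the synopsis that AUC over the 24 h dosing interval will be derived for each patient from the population PK model, and add this to section 8.3 as a named output for drug and metabolite.
3. If an observed partial AUC is kept, label it AUC(0–3 h) and describe it as early exposure. State that the time-zero value on Day 0 is taken as zero.
4. Observed Cmax and tmax may stay, with a note that they are limited to the sampled times.

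The cost is wording in two places and one added model output. The model and the pooling with earlier studies are already planned, so no new sample or visit is needed.
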